Blood sampling for antibody determination (approximately 10 mL) [#]		•					•	•				•	•				•			

Epoch	Screening	First study intervention administration						Second study intervention administration						Third study intervention administration					
		Visit 1 (First adm, A1)	Sentinel Safety phone contact	Reminder phone contact ¹	Home visit ²	Visit 2	Visit 3	Visit 4 (Second adm, A2) ³	Reminder phone contact ¹	Home visit ²	Visit 5	Visit 6	Visit 7 (Third adm, A3) ³	Reminder phone contact ¹	Home visit ²	Visit 8	Visit 9	Visit 10 (Safety phone contact)	
Type of contact	Screening Visit																		
Time points	Day -28 to Day -1	Day 1	Day 2	Day 4	Day 2 to Day 7	Day 8	Day 29	Day 57	Day 60	Day 58 to Day 63	Day 64	Day 85	Day 169	Day 172	Day 170 to Day 175	Day 176	Day 197	Day 337	
Sampling time points		Pre-A1				Post-A1	Post-A1	Pre-A2			Post-A2	Post-A2	Pre-A3	Post-A3		Post-A3	Post-A3	Post-A3	
PBMC extraction for monoclonal antibodies generation for Stage 2 participants only (approximately 50 mL)																	•		
Malaria Rapid Diagnostic Test ⁶	○	○																	
Safety assessments																			
Record any concomitant medications/vaccinations	•	•				•	•	•			•	•	•			•	•		
Record any intercurrent medical conditions		•				•	•	•			•	•	•			•	•		
Recording of solicited AEs in pDiary (Days 1 to 7 post-administration)		○ ⁴			○ ⁴			○ ⁴		○ ⁴			○ ⁴		○ ⁴				
Transcription of solicited AEs in the eCRF by the Investigator or delegate		•			•		•				•		•			•			

Epoch	Screening	First study intervention administration						Second study intervention administration						Third study intervention administration					
		Visit 1 (First adm, A1)	Sentinel Safety phone contact	Reminder phone contact ¹	Home visit ²	Visit 2	Visit 3	Visit 4 (Second adm, A2) ³	Reminder phone contact ¹	Home visit ²	Visit 5	Visit 6	Visit 7 (Third adm, A3) ³	Reminder phone contact ¹	Home visit ²	Visit 8	Visit 9	Visit 10 (Safety phone contact)	
Type of contact	Screening Visit	Day -28 to Day -1	Day 1	Day 2	Day 4	Day 2 to Day 7	Day 8	Day 29	Day 57	Day 60	Day 58 to Day 63	Day 64	Day 85	Day 169	Day 172	Day 170 to Day 175	Day 176	Day 197	Day 337
Time points	Sampling time points	Pre-A1				Post-A1	Post-A1	Pre-A2			Post-A2	Post-A2	Pre-A3	Post-A3		Post-A3	Post-A3	Post-A3	
Recording of unsolicited AEs (Days 1 to 28 post-administration)		○				○		○			○		○		○				
Transcription of unsolicited AEs in the eCRF by the Investigator or delegate		●				●	●	●			●	●	●		●	●			

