An additional 20 mL for assay development will be taken in Stage 1 on Day 85 from the participants who have given specific consent.

§ Out-of-window vaccination is not allowed.

¹ For literate participants in Europe/Africa only

² For illiterate participants in Africa only

³ The pre 2nd and 3rd vaccination screening in Malawi could take more than a day, necessitating additional site visits but not more than 72 hours prior to the actual receipt of the vaccination.

⁴ For illiterate participants, pDiary cards will be completed by the site field worker.

⁵ For illiterate participants, pDiary cards can be returned by the field worker at the end of the 7 days after administration.

⁶ For Malawi (Stage 2) only, subjects who test positive for malaria at Screening will be temporarily excluded (even if asymptomatic) and enrollment/first vaccination delayed until a negative malaria highly sensitive RDT is available. Treatment will also be provided for such prospective participants at the Investigator's discretion according to local guideline. For subsequent vaccinations, malaria RDT testing will only be performed if participants have symptoms suggestive of malaria.

⁷ Home visit for safety follow-up will take place only on Day 2.

Table 2 Intervals Between Study Visits

Interval	Planned visit interval	Allowed interval range
Screening (Day -28) → Visit 1 (Day 1)	Up to 28 days*	Up to 28 days*
Visit 1 (Day 1) → Visit 2 (Day 8)	7 days	7-10 days
Visit 1 (Day 1) → Reminder phone call 1 (Day 4)	3 days	1-3 days
Visit 1 (Day 1) → Visit 3 (Day 29)	28 days	28-33 [#] days**
Visit 1 (Day 1) → Visit 4 (Day 57)	56 days	52-62 days**
Visit 4 (Day 57) → Visit 5 (Day 64)	7 days	7-10 days
Visit 4 (Day 57) → Reminder phone call 2 (Day 60)	3 days	1-3 days
Visit 4 (Day 57) → Visit 6 (Day 85)	28 days	28-33 [#] days**
Visit 4 (Day 57) → Visit 7 (Day 169)	112 days	110-126 days**
Visit 4 (Day 57) → Visit 7 (Day 169)	112 days	110-140 ^{\$} days**
Visit 7 (Day 169) → Visit 8 (Day 176)	7 days	7-10 days
Visit 7 (Day 169) → Reminder phone call 3 (Day 172)	3 days	1-3 days
Visit 7 (Day 169) → Visit 9 (Day 197)	28 days	28-33 [#] days**
Visit 7 (Day 169) → Visit 10 (Day 337)	168 days	154-182 days

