3.0 OBJECTIVES AND ENDPOINTS

Table 3 Study Objectives and Endpoints

Objectives	Endpoints
Primary	

 • To evaluate the safety and reactogenicity profile of GSK Vaccines Institute for Global Health (GVGH) invasive nontyphoidal Salmonella-typhoid conjugate vaccine (iNTS-TCV) vaccine in healthy European/African adults 	
 • Number of participants in Europe/Stage 1 with solicited administration site and systemic events during 7 days after each study intervention administration (ie, on the day of study intervention administration and the 6 subsequent days) occurring at Day 1, Day 57, and Day 169, by study intervention group • Number of participants in Europe/Stage 1 with unsolicited adverse events (AEs) during 28 days after each study intervention administration (ie, on the day of study intervention administration and the 27 subsequent days) occurring at Day 1, Day 57, and Day 169, by study intervention group • Number of participants in Europe/Stage 1 with serious adverse events (SAEs) from first study intervention administration (Day 1) to 28 days after third study intervention administration (Day 197), by study intervention group • Number of participants in Europe/Stage 1 with AEs/SAEs leading to withdrawal from the study and/or withholding doses of study intervention, from first study intervention administration up to 28 days after third study intervention administration (Day 1 to Day 197), by study intervention group • Number of participants in Europe/Stage 1 with deviations from normal or baseline values for hematological, renal, and hepatic panels test results at 7 days after each study intervention administration (Day 8, Day 64, and Day 176) and at 28 days after each study intervention administration (Day 29, Day 85, and Day 197), by study intervention group • Number of participants in Africa/Stage 2 with solicited administration site and systemic events during 7 days after each study intervention administration (ie, on the day of study intervention administration and the 6 subsequent days) occurring at Day 1, Day 57, and Day 169, by study intervention group • Number of participants in Africa/Stage 2 with unsolicited AEs during 28 days after each study intervention administration (ie, on the day of study intervention administration and the 27 subsequent days) occurring at Day 1, Day 57, and Day 169, by study intervention group • Number of participants in Africa/Stage 2 with SAEs from first study intervention administration (Day 1) to 28 days after third study intervention administration (Day 197), by study intervention group • Number of participants in Africa/Stage 2 with AEs/SAEs leading to withdrawal from the study and/or withholding doses of study intervention, from first study intervention administration up to 28 days after third study intervention administration (Day 1 to Day 197), by study intervention group

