		2	Invasive nontyphoidal Salmonella-generalized modules for membrane antigens vaccine (iNTS-GMMA) and Typhoid conjugate vaccine (TCV) low doses	4	18 - 50 years	iNTS-GMMA low dose	iNTS-GMMA low dose	iNTS-GMMA low dose	
		3	Placebo_Step 1	2	18 – 50 years	TCV low dose	TCV low dose	TCV low dose	X
	Step 2 (40 participants)	4	iNTS-TCV full dose_1	16	18 – 50 years	Placebo	Placebo	Placebo	X
		5	iNTS-GMMA and TCV full doses_1	16	18 - 50 years	Saline	Saline	Saline	
		6	Placebo_Step 2	8	18 – 50 years	iNTS-TCV full dose	iNTS-TCV full dose	iNTS-TCV full dose	X
		7				Saline	Saline	Saline	
		8				Placebo	Placebo	Placebo	X
		9				Saline	Saline	Saline	

Study groups	Number of participants	Age (Min-Max)	Study interventions first administration	Study interventions second administration	Study interventions third administration	Blinding	
			Visit 1→Visit 10 (Observer-blind)*				
Stage 2 (105 participants)	7 iNTS-TCV full dose_2	45	18 – 50 years	iNTS-TCV full dose	iNTS-TCV full dose	iNTS-TCV full dose	X
				Saline	Saline	Saline	
	8 iNTS-GMMA and TCV full doses_2	45	18 - 50 years	iNTS-GMMA full dose	iNTS-GMMA full dose	iNTS-GMMA full dose	X
	9 Control_Stage 2	15	18 – 50 years	TCV full dose	TCV full dose	TCV full dose	X
				Menveo	Boostrix	Typhim Vi	
				Saline	Saline	Saline	

* The Sponsor representatives are unblinded after Visit 9 is completed for all subjects.

Blood samples will be collected:

- For selected hematology, biochemistry, viral serologic analyses, and human leukocyte antigen B27 (HLA-B27) testing, as part of the Screening. HLA-B27 testing will be done in Stage 1 only.
- For selected hematology and biochemistry analyses, before each study intervention administration and at 7 and 28 days after each study intervention administration, from all participants.
- For immunological assays, before and 28 days after each study intervention administration, from each randomized participant.
- An additional 20 mL for assay development will be taken in Stage 1 on Day 85 from the participants who have given specific consent.
- For peripheral blood mononuclear cells extraction for monoclonal antibodies generation at Visit 9 (for Stage 2 only)

Data will be collected through standardized electronic Case Report Forms (eCRFs). The collection of solicited administration site and systemic events will be done through a participant paper diary (pDiary).

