4.5 Study Holding Criteria

4.5.1 Study Holding Rules

Holding rules will be introduced to ensure a well-controlled exposure to the investigational candidate vaccine and to prevent participants from being exposed to any unnecessary safety risks in this FIH study. The holding rules will point attention to safety signals and indicate requirements for formal committee reviews that will decide whether additional participants can be exposed to the study intervention if particular criteria are met. Study holding rules are defined in [Table 5](#).

Holding rule 1 and 2c (threshold ≥ 1) will be assessed by the Investigator on a continuous basis irrespective of the number of enrolled participants and meeting any of these holding rules will trigger a hold of study intervention administration irrespective of number of enrolled participants and/or timing of the event relative to study intervention administration. Holding rule 2 (2a-b) and 1d.2 in Stage 2 (threshold ≥ 2) will be assessed during the safety evaluations on blinded or unblinded data.

These holding rules have been written under the assumption that the safety data from all participants will be available. If the data from some participants are not available (eg, in case a participant is lost to follow-up), then the holding rules will be assessed on a pro-rata basis.

If the Investigator becomes aware of a holding rule being met, he/she must suspend administration of the study intervention and inform the Sponsor's delegate immediately (holding rules 1a-d and 2c).

However, for the other holding rules (1d.2 in Stage 2, 2a and 2b) which have a threshold ≥ 2 , the Investigator will inform the Sponsor's delegate immediately, without suspending the administration of the study intervention.

The Sponsor's delegate will inform the Investigator if holding rules 1d.2 in Stage 2 and 2a-b are met.

The following communication sequence must be followed:

- The concerned site staff has to put study intervention administration on hold.
- The concerned site staff must immediately inform IQVIA CRA and Medical Monitor (contact details will be provided in a separate document) via email and phone communication who will in-turn inform the GVGH Study Responsible Project Physician.
- All informed site staff will confirm to their local contact that action has been taken providing appropriate documentation to GVGH through the IQVIA CRA and Medical Monitor.

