- GSK will further evaluate the case with the iSRC and GSK Global Safety Board and will take the decision to stop or to restart the study intervention administration. GVGH project physician will inform the IQVIA project lead of the decision and the rationale for the decision and all site staff will be informed about that final decision by IQVIA project lead.

Table 5 Study Holding Rules

Events	Number or % of participants needed to pause administration of study intervention	
	Stage 1 Step 1 and Step 2	Stage 2
1a Death or any life-threatening SAE regardless of causality	≥1	≥1
1b Any non-life-threatening SAE that cannot be reasonably attributed to another cause other than study intervention administration	≥1	≥1
1c Any withdrawal from the study (by Investigator or participant request) following a Grade 3 AE that cannot be reasonably attributed to another cause other than study intervention administration	≥1	≥1
1d.1 Any administration site or general solicited event leading to hospitalization, OR Necrosis at the injection site, each within the 7-day (Days 1 to 7) post-administration period	≥1	≥1
1d.2 Fever >40°C (104°F) within the 7-day (Days 1 to 7) post-administration period	≥1	≥2
2a Any Grade 3 solicited administration site event (lasting 48 h or more) in an investigational group, within the 7-day (Days 1 to 7) post-administration period	≥2	NA
2b Any Grade 3 solicited general AE (lasting 48 h or more) in an investigational group, within the 7-day (Days 1 to 7) post-administration period	≥2	NA
2c Any Grade 3 unsolicited AE in an investigational group, that can be reasonably attributed to the study intervention administration, within the 7-day (Days 1 to 7) post-administration period or Any Grade 3 abnormality in prespecified hematological or biochemical laboratory parameters in an investigational group within the 7-day (Days 1 to 7) post-administration period	≥1	NA

Abbreviations: AE = adverse event; h = hours; SAE = serious adverse event; NA = not applicable

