8.3.5 Solicited Adverse Events

The solicited administration site and systemic events that will be collected during the 7-day follow-up period after each administration (ie, from Day 1 to Day 7, from Day 57 to Day 63, and from Day 169 to Day 175) are presented in [Table 17](#).

The intensity of the solicited AEs will be assessed as described in [Table 18](#).

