In Step 2, a second sentinel of 10 participants vaccinated on consecutive days. They will receive a phone call for safety surveillance on the day following the first study intervention administration (Day 2), before proceeding with study intervention administration in the subsequent participants. The remaining 30 participants will be vaccinated at least 60 minutes apart.

Likewise, in Stage 2, the first 21 participants will receive the study interventions sequentially, at least 60 minutes apart, with a safety phone call/home Visit the day after administration for safety surveillance.

All 155 participants in the study (Stage 1 and Stage 2) will be closely monitored at the site for at least 60 minutes post-administration for safety surveillance.

Seven days after the first study intervention administration in the low dose cohort (Step 1) in Stage 1 is completed, an iSRC will receive a summary of all available safety data (solicited administration site events and systemic events, unsolicited AEs and SAEs) and listings of hematology and blood chemistry test values obtained following the first study intervention administration (baseline and 7 days after study intervention administration). Based on evaluation of the safety data (review #1, [Table 14](#)), the iSRC will make a recommendation, as to whether the next stage of the trial (Stage 1/Step 2), when the administration of the full dose of the study interventions to the study participants, should start.

Seven days after all participants in Stage 1/Step 1 have received their second study intervention, there will be an iSRC review of all safety data collected up to day 7 after second administration (Day 64) in Step 1 (review #2, [Table 14](#)). If there is no safety concern with any of the investigational groups, the second study intervention administration in Stage 1/Step 2 can commence.

There will be another iSRC data review 28 days after the second administration in Stage 1/Step 2 (review #3, [Table 14](#)). In the case of a favorable review, recruitment of participants in Stage 2 in Africa can commence.

All the participants in Stage 1 will complete the trial according to the schedule. A final safety evaluation of all data collected in Stage 1 will be performed once the study is completed.

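### Stage 1 holding rule 2c counts Grade 3 laboratory results on Days 1 to 7, but the first scheduled post-dose draw is Day 8, so it is unclear whether that result stops dosing

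*Protocol*

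**What the plan says.** Table 5 in Protocol Section 4.5.1 sets rule 2c at one or more participants in both steps of Stage 1 and marks it not applicable in Stage 2. Its laboratory limb reads: "Any Grade 3 abnormality in prespecified hematological or biochemical laboratory parameters in an investigational group within the 7-day (Days 1 to 7) post-administration period". The text before the table has the Investigator assess 2c continuously and suspend dosing when it is met. It adds that a hold then follows "irrespective of number of enrolled participants and/or timing of the event relative to study intervention administration".

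Safety blood is scheduled in Section 4.1.2 (list after Table 4): "For selected hematology and biochemistry analyses, before each study intervention administration and at 7 and 28 days after each study intervention administration". The primary laboratory endpoint in Table 3 dates the earlier of the two post-dose draws: "test results at 7 days after each study intervention administration (Day 8, Day 64, and Day 176". For the interval "Visit 1 (Day 1) → Visit 2 (Day 8", Table 2 plans 7 days and allows 7 to 10. It allows the same after the second and third doses.

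The protocol counts post-dose days in two ways:

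- **Dosing day is Day 1.** Table 1 has "Recording of solicited AEs in pDiary (Days 1 to 7 post-administration", and Section 8.3.5 gives the solicited period as "after each administration (ie, from Day 1 to Day 7, from Day 57 to Day 63, and from Day 169 to Day 175".
- **Dosing day is day 0.** Section 9.7 describes review #2 of the internal safety review committee (iSRC) as covering "all safety data collected up to day 7 after second administration (Day 64) in Step 1".

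**The concern.** Rule 2c is the only rule that turns a single Grade 3 laboratory value into an immediate suspension by the Investigator, and it applies in the first-in-human stage. If its window closes the day before the earliest scheduled sample, only an optional unscheduled test (Section 8.2.2) can trigger the laboratory limb. The other limb of 2c does not fill the gap: it has the same Days 1 to 7 limit and requires attribution to the study intervention.

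At stake is what the site does when a 7-day laboratory report arrives between iSRC reviews. Two Investigators reading the same text could reasonably act differently.

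**Working it through.** **The plan's own figures for rule 2c.** Section 4.5.1.1 gives operating characteristics for a threshold of one. The chance that the rule is met is 1 − (1 − p)^n.

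| n | p | Computed | Stated |
|---|---|---|---|
| 10 | 1% | not met 0.99^10 = 90.4% | more than 90% |
| 10 | 10% | met 1 − 0.90^10 = 65.1% | more than 65% |
| 40 | 1% | not met 0.99^40 = 66.9% | more than 70% |
| 40 | 2.5% | met 1 − 0.975^40 = 63.7% | more than 65% |

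The figures for 10 participants reproduce. Those for 40 fall short of the stated bounds, by 3.1 and 1.3 points; that is a separate matter. All of them presuppose that events can be counted, which for the laboratory limb depends on the window.

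**Window against draw, dosing day as Day 1.** The window runs from the dosing day to the dosing day + 6. The allowed draw runs from the dosing day + 7 to + 10.

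| Dose | Window | Allowed draw | Shared days |
|---|---|---|---|
| 1 | Days 1–7 | Days 8–11 | none |
| 2 | Days 57–63 | Days 64–67 | none |
| 3 | Days 169–175 | Days 176–179 | none |

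So 0 of 4 allowed draw days fall inside the window, for each of the three doses.

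**Window against draw, Section 9.7 count.** With Day 64 as day 7, the window is 1 to 7 days after dosing and the draw is at 7, 8, 9 or 10 days. One of the 4 allowed days falls inside. A compliant draw at 8 to 10 days is still outside.

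**The timing sentence in Section 4.5.1.** Read narrowly, it applies once a rule has been met, and the window is part of what meeting 2c means. Read broadly, it cancels the window, but it covers all of rule 1 as well and would then also cancel the explicit Days 1 to 7 limits in 1d.1 and 1d.2. The text does not say which reading is intended.

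**Samples covered.** Stage 1 investigational participants (Table 4): 4 + 4 + 16 + 16 = 40. Over three doses: 40 × 3 = 120 seven-day samples.

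**Doses a clear rule could stop.** Assume sentinel i is dosed on calendar day i, for i = 1 to 10. The first sentinel's draw falls on calendar day 8, 9, 10 or 11, when 3, 2, 1 or 0 sentinels have not been dosed before that day. In Step 2, 30 more participants follow the sentinels, and Table 14 places no iSRC review in between. If dosing runs on without a gap, an on-schedule draw from the first sentinel precedes up to 3 + 30 = 33 of 40 first full doses. Laboratory turnaround, which the documents do not give, would lower these counts.

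**The case against.** The strongest reply is that the rule was plainly meant to work. The dosing-day-as-Day-1 count is borrowed from solicited diary events; no passage applies it to laboratory data. For laboratory data the protocol calls Day 8, 64 and 176 the 7-day results, and Section 9.7 puts the 7-day values before the iSRC at review #1. A sensible Investigator would hold, and the timing sentence in Section 4.5.1 supports that. This shows what was probably intended, but it leaves draws at 8 to 10 days outside the tabulated limit and does not settle the two readings of the timing sentence.

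Other controls would still bring a Grade 3 result to attention:

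- Investigator review of every laboratory report (Section 8.3.2.1);
- use of the latest laboratory results to decide on doses 2 and 3 (Section 5.5);
- cumulative and ad hoc iSRC reviews (Section 9.7);
- blinded Safety Review Team monitoring (Table 15);
- rules 1a to 1c, which have no time window.

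That holds, and it limits the practical effect. None of these makes a single Grade 3 laboratory result a required suspension by the Investigator.

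Three further points stand. The 120 samples are those planned; only a Grade 3 result raises the question. Amendment 2 already mentions deviations observed in Stage 1, so few Stage 1 dosing decisions may remain, although the documents do not show that dosing was complete. The Study Reference Manual and the iSRC charter, which might instruct the site more clearly, were not available.

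**Conclusion.** The concern holds. Applied as tabulated with the dosing day as Day 1, no scheduled sample can trigger the laboratory limb of rule 2c. On the count in Section 9.7, only a draw taken exactly 7 days after dosing can. The protocol does not say which count governs laboratory results, or whether the timing sentence overrides the window.

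The effect is modest. It is confined to Stage 1, it arises only if a 7-day draw shows a Grade 3 value, and such a value would still be reviewed. What is missing is a clear instruction to suspend dosing. This rests on the protocol text alone and needs no assumed event rate. It is worth correcting because the rule protects a first-in-human cohort and the correction is small.

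**What to change.** Change only the laboratory limb of rule 2c in Table 5. In place of the Days 1 to 7 limit, let it count a Grade 3 value in any sample taken after dosing, up to and including the 7-day post-dose visit (Day 8, 64 or 176, no later than 10 days after dosing). The timing sentence in Section 4.5.1 can stay: the 7-day draw is then covered on either reading of it. The new wording does not decide the 28-day draw, which remains outside the tabulated limit. If Stage 1 dosing is complete, document instead how Grade 3 results on these draws were handled.

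The change adds no visits or samples. Its cost is possibly a few more holds, each needing an iSRC evaluation. The documents give no Grade 3 rate, so the rates p below (per participant at one 7-day draw) are assumptions; the chance of at least one such result is 1 − (1 − p)^n.

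| p | Step 2, n = 32 | Step 1, n = 8 |
|---|---|---|
| 0.5% | 14.8% | 3.9% |
| 1% | 27.5% | 7.7% |
| 2% | 47.6% | 14.9% |
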